Antibodies to exenatide

Blood samples will be collected for the measurement of antibodies to exenatide according to the schedule presented in the Study Plan (Table 1, Section 6.2). Samples for determination of anti-exenatide antibodies will be analyzed by a selected laboratory on behalf of AstraZeneca, using an appropriate method.

Only samples from patients who were on active study treatment will be analyzed. Samples from patients not dosed with the relevant active study treatment will only be analyzed on a “for cause” basis, for eg, if there is suspicion that a patient has been dosed incorrectly.

The method details and results will be reported in a separate report appended to the CSR. Anti-exenatide antibody samples received by the analytical group will be disposed of after the anti-exenatide antibody report finalization or 6 months after issuance of the draft antibody report (whichever is earlier), unless requested for future analyses or in support of the development or conduct of the assay.

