12.6.7.2 Clinical laboratory evaluations

All hematology, clinical chemistry, and urinalysis results will be listed by treatment, patient, and visit, including scheduled and unscheduled/repeat measurements. Laboratory assessments that are outside of normal ranges will be flagged.

Baseline values, the values at each visit, and changes from baseline values will be summarized for each of the quantitative laboratory assessments by treatment.

Shift tables of hematology, clinical chemistry, and urinalysis results will be used to summarize changes from Baseline Visit 2 (Week 0) to Study Termination (Visit 11 [Week 62] or Early Termination), and to each intermediate visit.

Antibody to exenatide data will be listed and summarized. A shift table of antibodies to exenatide will be used to summarize the change from baseline Visit 2 (Week 0) to each scheduled measurement. A patient is said to have treatment-emergent antibodies to exenatide at a visit if the antibody test is positive after the first injection of study medication following a negative or missing antibody measurement prior to the first injection of study medication, or the titer is increased by at least 3 dilutions from a detectable measurement prior to the first injection of study medication. The incidence of treatment-emergent antibodies to exenatide will be summarized by study visit, as appropriate.

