4.2.4.1 Adverse event analysis

Adverse events (AE) will be classified in accordance to the Medical Dictionary for Regulatory Activities (MedDRA) dictionary. All adverse events will be coded using the latest available version of MedDRA by the database lock.

Treatment-emergent AEs (TEAE) are defined as AEs occurring after the first dose of study medication through the end of the treatment plus 7 days (or + 90 days for SAEs and other clinically significant or related AEs), including AEs collected after patients initiate glycemic rescue therapy.

AEs occurring after Study Termination but considered by the Investigator as clinically significant and as related to study medication or study procedure, and SAEs occurring within 90 days of the last administration of study medication or EQW if in the extension phase will be recorded on the AE eCRF and reported in the AE listing.

Any AE that is recorded as the reason for study discontinuation will be considered an adverse event leading to discontinuation (DAE) regardless of the date recorded. All DAEs will be reported regardless of when they occurred. Note, any AE that is a DAE under these rules will also count as an AE when reporting.

Off-treatment AEs will be defined for the following:

- Treatment completers to Week 52: An AE that occurs between Week 52 to Week 62 and starts the day after last dose of open-label EQW + 7 days (or + 90 days for SAEs and other clinically significant or related AEs). Only patients completing study medication to Week 52 will be considered. Patients completing study medication to Week 52 but who withdraw prior to Week 62 will also be included.
- Premature discontinuation: An AE that starts the day after last dose of study medication + 7 days (or + 90 days for SAEs and other clinically significant or related AEs), for patients who discontinue study medication before Week 24 or Week 52.

AEs for the combined periods are those that occur during the Treatment period or post-treatment.

AEs with a start date prior to the first administration of study medication will be classified as pre-treatment (non-treatment emergent).

AEs with a stop date prior to the date of the first administration of study medication will be classified as pre-treatment (non-treatment emergent) AEs.

In case of missing AE severity, AE causality, or AE seriousness, a worst-case approach will be used. For AE missing severity, the AE will be considered severe; for missing causality, the

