AE will be considered as possibly-related to study medication; for missing seriousness, the AE will be considered serious.

On-treatment AEs (TEAEs) will be summarized for 24-week controlled assessment period and 28-week extension period as defined below. Off-treatment AEs for treatment completers to Week 52 will be tabulated where required. Off-treatment AEs for patients who prematurely discontinued will be listed only.

An overall summary of number and percentage of patients experiencing at least 1 TEAE will be presented for EQW and PBO. The summary will be presented by study period (controlled assessment period and extension period). A summary of AEs during the Treatment period for patients with actual treatment EQW during the controlled assessment period will be provided. The AE summary will include the number and percentage of patients experiencing any AE, any SAE, any AE related to treatment per Investigator's discretion, any AE leading to treatment discontinuation, any AE leading to study withdrawal, and any fatal AE.

Additionally, all TEAEs will be summarized for each treatment group as follows:

- AEs summarized by SOC, PT, maximum intensity (Mild, Moderate, Severe), causality (Not related, Related), action taken, and outcome.
- SAEs summarized by SOC and PT, maximum intensity (Mild, Moderate, and severe), causality (Not related, Related).
- AEs leading to treatment discontinuation summarized by SOC and PT.
- Frequent AEs (AE with at least 5% incidence in any treatment) summarized by preferred term.
- Non-serious frequent AEs summarized by SOC and PT.
- Potentially immune-related AEs summarized by antibody status (positive versus negative), SOC and PT.
- Potentially immune-related AEs summarized by antibody titer (higher: ≥ 625 versus low: < 625), SOC and PT.
- Potentially immune-related injection site-related AEs summarized by SOC and PT.

Summaries by maximum intensity will be presented separately for the controlled assessment period (Safety analysis set) and extension period (subset of Safety patients who received open-label EQW during the extension period). All other AE summary tables will be presented by study period in a single table.

Potentially immune-related AEs will be identified using the PTs given in [Appendix B4](#).

Injection site-related AEs will be identified using AEs within higher-level term "Injection site reactions".

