4.2.4.6 Antibodies to exenatide

A patient is said to have treatment emergent antibodies to exenatide at a visit if the antibody test is positive after the first injection of study medication following a negative or missing antibody measurement prior to the first injection of study medication, or the titer is increased by at least 3 dilutions from a detectable measurement prior to the first injection of study medication.

Number and percentage of patients incidence of antibodies to Exenatide for the categories negative, any positive, low positive, and high positive will be summarized descriptively by visit for the safety analysis set, for the treatment period.

The primary efficacy endpoint HbA1c will be summarized by antibody status (negative, any positive, low positive, higher positive) and by visit to evaluate the effect of antibody formation on efficacy.

Descriptions of planned summaries of AEs by antibody status can be found in [Section 4.2.4.1](#). Antibodies to exenatide will be defined based on the highest antibody titer in each patient at any time during the on-treatment period.

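### Antibody status is fixed by the highest titre at any time on treatment, so immune-related adverse events from the placebo period, and other controlled-period events, can be sorted by antibodies that formed later

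*SAP*

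**What the plan says.** SAP 4.2.4.6 gives one definition of status: "Antibodies to exenatide will be defined based on the highest antibody titer in each patient at any time during the on-treatment period". Nothing ties that status to the date of an event or a visit.

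Two kinds of output use antibody status or titre.

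- **Adverse events (SAP 4.2.4.1).** One table is "Potentially immune-related AEs summarized by antibody status (positive versus negative), SOC and PT". Another is "Potentially immune-related AEs summarized by antibody titer", split at 625. Both are produced for each treatment group. On layout, the section says: "All other AE summary tables will be presented by study period in a single table". The events counted are treatment-emergent: "Treatment-emergent AEs (TEAE) are defined as AEs occurring after the first dose of study medication". For Group B that first dose is placebo.
- **HbA1c (SAP 4.2.4.6).** "The primary efficacy endpoint HbA1c will be summarized by antibody status (negative, any positive, low positive, higher positive) and by visit", with the stated aim of judging whether antibody formation affects efficacy.

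On assays, Protocol 6.4.5.5 says: "Only samples from patients who were on active study treatment will be analyzed". Other samples are run only for cause. Protocol 5.4.1 says the same.

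Protocol 12.6.7.2 asks for a shift table of antibodies from baseline to each scheduled measurement, and adds: "The incidence of treatment-emergent antibodies to exenatide will be summarized by study visit, as appropriate". SAP 4.2.4.6 repeats the definition of treatment-emergent antibodies. The incidence output it lists uses only the categories negative, any positive, low positive and high positive. It has no antibody shift table, and SAP Section 5 declares no change on this point.

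**The concern.** The event tables divide events by period but do not divide status by period. A patient carries one label, taken from the whole on-treatment period, into both the controlled-period and extension columns. An event can then be counted under antibody-positive although the patient had no detectable antibody, or had never received exenatide, when it happened.

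The placebo column is the clearest case. Its cells need not be empty. The preferred terms in SAP Appendix B4 include injection-site nodule, erythema and pruritus. Protocol 5.5.2 describes placebo as the same formulation without the active ingredient, and Protocol 6.4.10 expects nodules with sustained-release delivery. Reactions to the vehicle could therefore be displayed as if related to antibodies against a drug not yet given.

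At stake is whether these tables can help show that antibodies go with reactions, or with a weaker HbA1c response. A label that depends on later data obscures the order of the two.

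**Working it through.** The plan states no figure on this point, so there is none to reproduce. The check traces the rule through the definitions.

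**1. Which period sets the status.** SAP 3.6.5.2 defines the safety treatment period as the controlled and extension periods combined, ending 7 days after the last dose. SAP 4.2.4.6 does not define the on-treatment period separately for antibodies, so the combined period is the natural reading.

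**2. Which samples can make a patient positive.** From the visit lists in Protocol 6.2.3:

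| Visit | Antibody sample | Usable for status in Group A | Usable for status in Group B |
|---|---|---|---|
| Weeks 4, 8, 12 | Yes | Yes | Not assayed (placebo) |
| Week 18 | No | – | – |
| Week 24 | Yes | Yes | Not assayed; precedes first exenatide dose |
| Weeks 28, 40 | No | – | – |
| Week 52 or Early Termination | Yes | Yes | Yes, once on exenatide |
| Week 62 | Yes | No, at least 10 weeks after last dose | No, same reason |

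The notes to SAP Figure 1 place Group B's first exenatide dose at the Week 24 visit. Unless a for-cause assay is run, a Group B patient can become positive only from the Week 52 or Early Termination sample. That label then sorts the events of Weeks 0 to 24.

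**3. Share of time labelled positive before the first positive sample.** For a patient who completes and is first positive at week *t*, the share is *t*/52 of the whole treatment period and min(*t*, 24)/24 of the controlled period.

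| First positive sample | Share of 52 weeks | Share of controlled period |
|---|---|---|
| Week 4 | 4/52 = 7.7% | 4/24 = 16.7% |
| Week 8 | 8/52 = 15.4% | 8/24 = 33.3% |
| Week 12 | 12/52 = 23.1% | 12/24 = 50% |
| Week 24 | 24/52 = 46.2% | 24/24 = 100% |
| Week 52 | 52/52 = 100% | 24/24 = 100% |

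For Group B (77 × 2/7 = 22 patients planned), time before any exenatide is 24/52 = 46.2% of the treatment period and all of the controlled period. These are shares of time, not of events. The first positive sample is also later than seroconversion, so time before it is not all time before antibodies.

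**4. Direction of the bias, on assumed inputs only.** A simulation had no link between antibodies and events and 400,000 patients per scenario. It assumed that 30%, 50% or 70% seroconvert, uniformly over the 24 weeks after starting exenatide. Dropout was 10% or 20% per 24 weeks, and the expected number of events was 0.2 or 0.5 per 52 weeks. Samples followed the schedule above, with an Early Termination sample. Over the full 52 weeks, the incidence ratio of ever-positive to all other patients was 1.05 to 1.29 in Group A and 1.13 to 1.56 in Group B. It exceeds 1 because patients who stay longer have more chance both of a positive sample and of an event. This shows direction only. The inputs are not from the documents, the ratios are not split by period as the planned tables are, and the Group B comparison group includes patients who left without any assayed sample.

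**The case against.** The strongest reply is that the on-treatment period is undefined for antibodies, and SAP 4.2.4.1 summarises on-treatment events separately by period. If status is also set period by period, nothing is carried back. That reading is possible, but Group B would then have no assayed status in the controlled period, and the SAP does not say how to show such patients. Either reading needs new text.

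Four further limits stand.

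- A reader might infer that all adverse events are affected. They are not: only the potentially immune-related ones are tabulated by status or titre.
- A reader might infer that HbA1c at Week 24 will be grouped by titres reached up to Week 52. The text does not settle this. The defining sentence follows the one about adverse events, and the HbA1c summary is by visit, which could mean visit-specific status.
- A reader might take the simulated ratios as the expected bias. They are not, and even as an illustration the precision is poor. With 55 exenatide patients, 38 positive and 17 negative, and an assumed 30% incidence in each, the standard error of the log ratio is √(0.7/(0.3 × 38) + 0.7/(0.3 × 17)) = 0.446. The 95% interval around a true ratio of 1 is then about 0.42 to 2.4.
- A reader might conclude that patients who stop early are simply classed as negative. This is partly handled, because Early Termination includes an antibody sample.

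The obvious remedy, counting an event as positive only from the first positive sample, does not work here. With no sample between Week 24 and Week 52 or Early Termination, it would place essentially all of Group B's extension events under negative, even in patients who seroconverted soon after Week 24.

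On the protocol outputs, antibody incidence by visit remains in the SAP, and the protocol asks for the treatment-emergent version only as appropriate. Patients with earlier exenatide or GLP-1 agonist use are excluded, so the two incidences are likely to be close. The missing shift table is a plain undeclared omission.

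**Conclusion.** The point holds for the tables of potentially immune-related events by antibody status and by titre. On the natural reading, Group B's placebo-period events are sorted by antibodies formed later on exenatide, and controlled-period events in Group A can be sorted by titres first reached in the extension. This rests on two things: the combined-period reading, and placebo-period samples staying unassayed apart from for-cause testing.

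For HbA1c, the point is an ambiguity to be resolved, not a demonstrated error.

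The bias in the event comparison cannot be derived from the documents, which give no seroconversion rate, timing or immune-related event rate. The antibody outputs are descriptive and lie outside the testing hierarchy in SAP 4.2.3.2. A reader might infer that the efficacy conclusion is in doubt; nothing supports that. The harm is to the interpretation of the immunogenicity tables. It merits correction because the remedy needs no new data.

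**What to change.** Amend SAP 4.2.4.1 and 4.2.4.6 as follows.

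1. Restrict the tables of events by antibody status or titre to exenatide-exposed time, with no antibody split for placebo in the controlled period.
2. For the controlled-period column, define status from samples up to Week 24. For the extension column, define it from samples through end of treatment.
3. State that HbA1c at a visit is grouped by the highest titre up to that visit. Patients with no assayed sample on exenatide by then should be shown as not assessed. In Group B that includes Weeks 28 and 40.
4. If onset relative to seroconversion is wanted, add a supportive split of events into before the last negative sample, between the last negative and first positive samples, and after the first positive sample. This keeps the 28-week sampling gap visible and avoids forcing a strict cut-off.
5. Restore the treatment-emergent incidence by visit and the antibody shift table of Protocol 12.6.7.2, or declare their removal in SAP Section 5. Treat Group B's unassayed result before exenatide as missing, which the existing definition of treatment-emergent antibodies already allows.

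The cost is SAP wording, one extra date-based flag and smaller cells, which matters with about 55 and 22 patients. Item 2 still leaves the order of events and antibodies unresolved within a period; only item 4 addresses that, and only as closely as the sampling allows.

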4.2.4.7 Hypoglycemia

All summaries of hypoglycemic events will be presented for both the controlled assessment period (Safety analysis set) and the extension period (subset of Safety patients who received open-label EQW during the extension period). Hypoglycemic events will be presented as events occurring after the first dose of study medication through the end of the treatment plus 7 days.

The number and percentage of patients with hypoglycemic events, per the HYAEBO eCRF, along with the number of events will be summarized by severity (mild, moderate, severe or unknown) defined as follows,

Mild: Usually transient, requires no special treatment, and does not interfere with the patient's daily activities.

Moderate: Usually causes a low level of inconvenience or concern to the patient and may interfere with daily activities but is usually ameliorated by simple therapeutic measures.

Severe: Requires the assistance of another person to obtain treatment (e.g., intravenous glucose, intramuscular glucagon, or oral carbohydrate) for the event.

Additionally, hypoglycemia will be programmatically classified as major, minor, or other hypoglycemia as follows,

- Major hypoglycemia is defined as:

An event that results in loss of consciousness, seizure, or coma (or other mental status change consistent with neuroglycopenia in the judgment of the Investigator or physician), and which resolves after administration of glucagon or glucose

Or

An event that requires third party assistance to resolve because of severe impairment in consciousness or behavior (whether or not symptoms of hypoglycemia are detected by the patient) and is associated with a plasma or capillary glucose concentration of <3 mmol/L (54 mg/dL)

- Minor hypoglycemia is a non-major hypoglycemia event that has symptoms consistent with hypoglycemia and had a glucose value of <3 mmol/L (54 mg/dL) prior to treating the episode.
- If a hypoglycemia event does not meet the criteria for a major or minor event described above, it will be classified as other.

The number and percentage of patients with hypoglycemic events, along with the number of events will be summarized by major/minor classification.

Hypoglycemic events will also be programmatically classified into three levels⁶ according to severity:

- Level 1: A glucose alert value of 3.9 mmol/L (70 mg/dL) or less.
- Level 2: A glucose level of <3.0 mmol/L (<54 mg/dL) is sufficiently low to indicate serious, clinically important hypoglycemia
- Level 3: Severe hypoglycemia, as defined by the ADA^{7, 8}, denotes severe cognitive impairment requiring external assistance for recovery

The number and percentage of patients with hypoglycemic events based on the aforementioned classification, along with the number of events will be summarized by level.

The number and percentage of patients with any hypoglycemic event by baseline insulin and sulfonylurea use will be summarized according to the following categories:

- Any (includes patients with and without insulin/sulfonylurea use at baseline)
- Insulin and sulfonylurea use at baseline
- Insulin only
- Sulfonylurea only

- No insulin or sulfonylurea

Key patient information for hypoglycemic events will be presented.

4.2.5 Mixed meal sub-study

Baseline values, the observed values and change from baseline values will be summarized for C-peptide, glucose, glucagon and insulin results, over timepoints for the Standardized mixed meal test evaluable analysis set. A listing by individual patients' data will also be reported.

4.3 Conventions

4.3.1 Visit assignments for efficacy variables

All visits scheduled during the 24-week controlled assessment and 28-week extension period should occur within ± 2 days of the scheduled date relative to Visit 2 (Week 0) per the CSP.

Patients do not always adhere strictly to the visit timing in the CSP. Therefore, the designation of visits during the treatment period will be based on the day of evaluation relative to the start of the controlled assessment period (day of study medication = Day 1) rather than the nominal visit recorded in the eCRF.

To assign a measurement to a Week t during the study, the first step is to select all measurements falling within the study period. Mutually exclusive relative day windows are used to determine the Week t measurement. These relative day windows are defined to provide derived visits that correspond to the post-baseline time points specified in the CSP. Some restrictions may exist on some laboratory assessments to be included in efficacy analyses. These restrictions will be reflected in the relative day ranges. Visit windows for efficacy variables are listed below.

Visit windows will not be used for Visit 11 (Week 62) and data will be presented per the visit label.

Table 3.1 Visit Windows: HbA1c, Body weight, BMI, Rescue medication (based on start date of medication) and blood pressure

Visit	Analysis Visit	Week	Period	Target Day	Day range
2	0	0	CAP	1	Baseline
3	1	4	CAP	29	2-42
4	2	8	CAP	57	43-70
5	3	12	CAP	85	71-105
6	4	18	CAP	127	106-147
7	5	24	CAP	minimum (last day of CAP or 169)	148 to last day of CAP

Visit	Analysis Visit	Week	Period	Target Day	Day range
8	6	28	EP	maximum (last day of CAP+1 or 197)	last day of CAP +1 to 238
9	7	40	EP	281	239-322
10	8	52	EP	minimum (last day of EP or 365)	323 to last day of EP

CAP: Controlled assessment period. EP: Extension period.

Table 3.2 Visit Windows: Fasting plasma glucose, Fasting Insulin, Plasma Exenatide

Visit	Analysis Visit	Week	Period	Target Day	Day range
2	0	0	CAP	1	Baseline
3	1	4	CAP	29	2-42
4	2	8	CAP	57	43-70
5	3	12	CAP	85	71-126
7	5	24	CAP	minimum (last day of CAP or 169)	127 to last day of CAP
10	8	52	EP	minimum (last day of EP or 365)	last day of CAP +1 to last day of EP

CAP: Controlled assessment period. EP: Extension period.

Table 3.3 Visit Windows: Fasting Lipids

Visit	Analysis Visit	Week	Period	Target Day	Day range
2	0	0	CAP	1	Baseline
5	3	12	CAP	85	2-126
7	5	24	CAP	minimum (last day of CAP or 169)	127 to last day of CAP
10	8	52	EP	minimum (last day of EP or 365)	last day of CAP +1 to last day of EP

CAP: Controlled assessment period. EP: Extension period.

Table 3.4 Visit Windows: Total daily insulin

Visit	Analysis Visit	Week	Period	Target Day	Day range
2	0	0	CAP	1	Baseline: -7 to -1
3	1	4	CAP	29	23 to 29
4	2	8	CAP	57	51 to 57
5	3	12	CAP	85	79 to 85
6	4	18	CAP	127	121 to 127
7	5	24	CAP	minimum (last day of CAP or 169)	[min (last day of CAP, 169) – 7] to [min (last day of CAP, 169) - 1]
8	6	28	EP	maximum (last day of CAP+1 or 197)	[max (last day of CAP +1, 197) – 6] to [max (last day of CAP +1, 197)]
9	7	40	EP	281	275-281
10	8	52	EP	last day of EP	(last day of EP – 6) to (last day of EP)

CAP: Controlled assessment period. EP: Extension period.

If a patient discontinues study medication prior to the upper day range specified in the Table 3.4 window, the average total daily insulin will not be calculated for that visit.

